# 9. Demographic, Other Baseline Characteristics and Medication

### 9.1. Subject Disposition and Withdrawals

Subject disposition will be presented for all subjects, which include the following:

- Number of subjects enrolled
- Number of screened and reason for screen failure
- Number (%) of subjects in the Safety Set
- Number (%) of subjects who discontinued study prematurely and their reason during open label
- Number (%) of subjects in the Pharmacokinetic Set
- Number (%) of subjects randomized (Intent-to-Treat Set)

Among the randomized subjects, the following will be summarized:

- Number (%) of subjects in the Modified Intent-to-Treat Set
- Number (%) of subjects in the Per-Protocol Set
- Number (%) of subjects who completed the study
- Number (%) of subjects who discontinued study prematurely and their reason during R/WD

A separate by-subject listing of subject disposition and withdrawal will also be provided. Subjects who screen failed will be listed along with the date and reason for the screen failure.

Randomized subjects not included in an analysis set and their reason for exclusion will be summarized and listed.

### 9.2. Demographic and Baseline Characteristics

Demographics and other baseline characteristics will be summarized for the Safety, Modified Intent-to-Treat, and Intent-to-Treat Sets by randomized treatment and overall. Summary statistics and by-subject listings will be provided.

Demographics and baseline characteristics will include age, sex, ethnicity, weight, height, body mass index (BMI), weight z-score, height z-score, BMI z-score for children/adolescents and for adults. Medical History and Concomitant Diseases

### 9.3. Medical History and Concomitant Diseases

Medical history will be summarized by system organ class (SOC) and preferred term using the number and percentage of subjects with each term and will be produced from the Safety Set. Medical history will be sorted alphabetically by SOC and in descending order of number of subjects per preferred term within each SOC.

Medical history will be coded using the Medical Dictionary for Regulatory Activities (MedDRA) version 25.0 or higher.

A separate by-subject listing of medical history will also be provided.

This document is confidential.

SAP text Version: SAP text 3.0 6-Dec-2023

Controlled Document ID: 3903A.02, Effective Date 31-Aug-2020

#### 9.4. Medication

Prior and concomitant medications will be summarized based on classification using the Anatomical Therapeutic Chemical (ATC) classification and preferred drug name from the World Health Organization Drug Dictionary, version Mar 2019, or later.

#### 9.4.1. Prior Medication

Prior medications are defined as medications entered in the eCRF that either start, or end before the first dose of study medication. Prior medications will be summarized using the number and percentage of subjects by ATC (4th level, or most specific level available if 4th level is unavailable) and preferred drug name for the Safety Set.

Prior medications which continue after first dose of study medication will also be classified as a concomitant medication.

#### 9.4.2. Concomitant Medication

Concomitant medications are defined as medication on the eCRF that are taken on or after or are ongoing at the start date of dosing. Concomitant medications will be summarized using the number and percentage of subjects by ATC (4th level, or most specific level available if 4th level is unavailable) and preferred drug name for the Safety Set.

# 9.5. Extent of Exposure

Duration of exposure in days will be summarized using descriptive statistics by open-label stabilization and double-blind randomized withdrawal period (by treatment group and overall) and overall. The duration of exposure in days will also be categorized (<7,  $\ge$ 7,  $\ge$ 14,  $\ge$ 28,  $\ge$ 56,  $\ge$ 84,  $\ge$ 91,  $\ge$ 98,  $\ge$ 105,  $\ge$ 112,  $\ge$ 126,  $\ge$ 140,  $\ge$ 154,  $\ge$ 168), and tabulated.

A listing including study drug administration information from the eCRF will be presented.

### 9.6. Treatment Compliance

Subjects are expected to take study medication as per dosing regimen specified in section 4.5.

Subjects will be considered compliant overall for study medication if the compliance is ≥80%. Descriptive statistics (number of subjects, mean, SD, minimum, median, and maximum) for number of actual tablets taken and number of expected tablets taken will be summarized by treatment group. Treatment compliance will be summarized descriptively as a continuous variable as well as a categorical variable (<80%, 80%-120%, >120%) by treatment group.

# 10. Efficacy

# 10.1. Primary Efficacy Endpoint and Analysis

The YGTSS is a clinician-rated, multi-dimensional instrument for assessing tic symptoms in children and adults with TD. It includes a semi-structured interview with either caregivers (for subjects <18 years of age) or adult subjects (≥ 18 years of age) and clinical observations that assess tic and tic-related impairment severity over the previous week. Every attempt should be made, per subject, to complete interview by the same caregiver or subject and same rater for all visits.

Both motor and vocal tics are assessed for symptom number, frequency, intensity, complexity, and interference on a 0–5 Likert scale. Scores from each dimension are totaled to reflect the severity of motor tics (range 0–25), vocal tics (range 0–25) and combined tics, or Total Tic Score (-TSS) (range 0–50). A separate tic-related impairment scale, scored from 0 to 50, is also included and calculated for the Global Severity score (-GS).

YGTSS will be assessed at Screening, Baseline and at Weeks 4, 8, 12, 13, 14, 15, 16, 18, 20, 22, 24 and 7 day follow up visit.

The primary efficacy endpoint is time from Randomization to Relapse defined as a loss of ≥ 50% of the improvement experienced on the YGTSS-TTS from Baseline to the last visit in the open-label Stabilization period (Week 12), or initiation of additional medications to treat symptoms of TD, or requirement of hospitalization for worsening symptoms of TD in subjects ≥ 6 and < 18 years during the double-blind R/WD period for ecopipam compared to placebo. Data from subjects who complete or discontinue from the double-blind R/WD period without Relapse will be considered as censored observations. The log rank test will be the primary test of statistical significance. Kaplan-Meier curves will be used to compare the times to relapse between the treatment groups. The hazard ratio and its 95% confidence interval (CI) will be estimated from the Cox proportional hazard model with treatment as a factor. The proportional hazards assumption will be evaluated graphically and analytically, for example by assessing martingale and Schoenfeld residuals and by modeling time-dependent covariates.

The analysis of the primary efficacy endpoint will be performed in the mITT (primary), ITT, and PP populations according to the randomized treatment.

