7.3. Treatment Assignment

Responders to ecopipam in the open-label Stabilization period will be randomized 1:1 to either ecopipam or matching placebo for the R/WD period. Randomization assignment will be stratified by weight.

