# 4.3. Determination of Sample Size

The planned number of Relapse events for the double-blind R/WD Phase is 49 in children and adolescents. This number of events will provide 85% power to detect a difference between treatment groups, assuming a hazard ratio of 0.4 for Relapse and statistical testing at alpha level 0.05 (2-sided). Subject enrollment will stop around the time that 49 Relapse events among children and adolescents are anticipated to have occurred. The number of Relapse events among adults will not determine study completion.

Assuming the proportion of subjects who Relapse in the DB randomization phase is 65% in the placebo group and 34% in the ecopipam group, approximately 98 subjects (49 subjects per group) will be required to achieve this number of Relapse events.

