# 4.4. Treatment Assignment and Blinding

Eligible subjects will receive open label ecopipam tablets for up to 12 weeks. Subjects who qualify as Responders to ecopipam in the open-label Stabilization period will be randomized 1:1 to either ecopipam or matching placebo for the R/WD 12- week period. Randomization will be stratified by weight band (≥18 to ≤23 kg, >23 to ≤34 kg, >34 to ≤44 kg, >44 to ≤68 kg, >68 to ≤83 kg, >83 kg).

Throughout the study, subjects, caregivers, and all personnel involved with the conduct and interpretation of the study, including the subject, parents/guardians, investigators, site personnel, and sponsor staff will be blinded to the treatment codes. Randomization data will be kept strictly confidential, filed securely by an appropriate group with the Sponsor or Syneos and accessible only to authorized persons (e.g., Safety) until the time of unblinding.

A master list of all treatments and the subject numbers associated with them will be maintained electronically in the Interactive Web Randomization System (IWRS). The process to request a randomization code will be outlined in IWRS user manual. The site will be trained in this process, and it should be used only in an emergency. These codes should only be broken if knowledge of the subject's randomization code will affect his/her medical treatment. If possible, before breaking the blind, the Investigator should consult with the Sponsor to ascertain the necessity of breaking the code. The Investigator is to record the date and time of requesting the code and the reason for breaking the code.

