### 10.1.1. Sensitivity Analysis

To assess the robustness of the primary efficacy analysis, the following sensitivity analysis will be performed for the mITT and the ITT set:

Assume subjects who are lost to follow up or who discontinue the study for reasons other than Relapse or lack of efficacy meet the Relapse criteria. Their last non-missing date on study will be used as the date of Relapse. Relapse rate will be estimated using Kaplan-Meier methods and the difference between treatment arms will be tested using the log rank test. Cox proportional hazard model will be run with treatment as factor.

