#### Statistical analysis:

A secondary analysis will be performed irrespective of age. The analysis method will be the same as the primary efficacy analysis as described in Section 10.1.

10.2.2. Time from Randomization (Week 12) to a worsening by at least one category of the CGI-TS-S in subjects ≥ 6 and < 18 years for ecopipam compared to placebo during the double-blind, R/WD period

The Clinical Global Impression of Tourette Syndrome (CGI-TS) consists of two reliable and valid 7-item Likert scales used to assess severity and change in clinical symptoms. The severity scale (CGI-TS-S) ranges from 1 (Normal, not ill) to 7 (extremely ill). The improvement scale (CGI-TS-I) ranges from 1 (very much improved) to 7 (very much worse) with a score of 1 or 2 defining positive response.

The severity rating is based upon observed and reported symptoms, behavior, and function in the past seven days with the score reflecting the average severity level across the seven days. The efforts of peers, teachers and parents to assist, accommodate, or support the subject should be considered in overall severity.

Severity will be assessed at Screening, Baseline and at Weeks 4, 8, 12, 13, 14, 15, 16, 18, 20, 22 and 24. Improvement will be assessed at Baseline and at Weeks 4, 12, 13, 14, 15, 16, 18, 20, 22 and 24.

Sponsor: Emalex Biosciences, Inc.; Protocol No.: EBS-101-TD-301

The Severity scale ranges from: 1=normal, not at all ill; 2=borderline mentally ill; 3=mildly ill; 4=moderately ill; 5=markedly ill; 6=severely ill; 7=among the most extremely ill patients where the improvement scale ranges from: 1=very much improved; 2=much improved; 3=minimally improved; 4=no change; 5=minimally worse; 6= much worse; 7=very much worse."

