where  $\Phi(.)$  denotes the cumulative distribution function of the standard normal distribution, and  $z_{\alpha/2}$  denotes the  $1-\alpha/2$  quantile of the standard normal distribution, and  $Z_{int}$  is z-value at interim analysis, which can be obtained from the output of PROC LIFETEST in SAS. The  $Z_{int}$  can be derived from the reported Logrank statistics and the corresponding covariance matrix

Derivation:

$$Z_{int} = \frac{O - E}{\sqrt{V}} = \frac{\sum_{j} (O_j - E_j)}{\sqrt{\sum_{j} V_j}}$$

where,

 $O_i = d_{1i}$ , Number of subjects in Ecopipam who developed Relapse, at distinct time j

This document is confidential.

SAP text Version: SAP text 3.0 6-Dec-2023

Controlled Document ID: 3903A.02, Effective Date 31-Aug-2020

$$E_j = \left(\frac{Y_{1j}}{Y_j}\right) * d_j, \qquad d_j = d_{0j} + d_{1j}, \text{ total number of Relapses at time j, } Y_{1j} = \text{Number of subjects in Ecopipam at time } j,$$

 $Y_i$  = Number of subjects at risk at time j.

$$V_j = \frac{Y_{0j}Y_{1j}d_j(Y_j-d_j)}{Y_i^2(Y_j-1)}, Y_{0j} = \text{number of subjects at risk at time j at control arm,}$$

 $d_i = d_{0j} + d_{1j}$  total number of Relapses at both control arm and Ecopipam at time j.

Based on the results of the above conditional power and the promising zone approach [8], the DSMB may make the following interim decisions:

- If p-value based on Logrank test at interim analysis is less than 0.005 and other measures (e.g., hazard ratio) imply a benefit of ecopipam over placebo, it is recommended to stop the study for overwhelming efficacy.
- 2) If 50%<CP<85%, then increase the number of required events such that CP based on the adjusted events ≥85% or reach the maximum number of Relapse events allowed, defined as two times the planned Relapse events (49 x 2 = 98).
- 3) If condition power (CP)<20%, it is recommended to stop the study for futility.
- 4) If all other cases, continue this study as planned.

No adjustment of the final alpha level will be required, other than the alpha spending of the IA, based on the CP approach.

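### Randomization is stratified by weight band, but the log-rank tests, the Cox model and the interim statistic ignore the bands; stratifying them is a cheap improvement

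*SAP*

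**What the plan says.** SAP 4.4: "Randomization will be stratified by weight band", with six bands listed. Protocol 7.3 agrees: "Randomization assignment will be stratified by weight". Protocol 9.5 repeats it.

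For the primary endpoint, SAP 10.1 states: "The log rank test will be the primary test of statistical significance". No strata are named, and the hazard ratio is "estimated from the Cox proportional hazard model with treatment as a factor". Protocol 13.4.1 and the synopsis say the same. The analyses that follow inherit this:

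- SAP 10.1.1 (sensitivity): "Cox proportional hazard model will be run with treatment as factor".
- SAP 10.2.1 (secondary endpoint, all ages): "The analysis method will be the same as the primary efficacy analysis as described in Section 10.1". SAP 13 uses the same sentence for the interim.
- SAP 13: the interim Z is one "which can be obtained from the output of PROC LIFETEST in SAS". Its formula sums O-E and V over event times only, with no stratum index.

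Weight band appears in one adverse event table (SAP 12.1) but in no efficacy model. The repeated-measures models adjust for region and age group, and weight band is not an efficacy subgroup in SAP 8.6. No reason is given for leaving the strata out.

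**The concern.** Stratified randomization balances the arms within each band. If the band is prognostic, that balance removes some chance variation from the treatment comparison. The unstratified log-rank variance does not credit this, so it is too large and the test is conservative. Leaving out a prognostic factor also pulls the marginal hazard ratio towards 1. Both effects cost power; neither inflates the type I error.

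The documents do not show that weight band predicts Relapse, but they give two reasons why it might.

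- The placebo taper uses fixed 22.4 mg/day decrements from band-specific doses (SAP 4.5). From 33.6 mg that is 33.6/22.4 = 1.5, so about 2 steps; from 179.2 mg it is 179.2/22.4 = 8 steps. Step length is not stated.
- Weight in 6- to 17-year-olds presumably tracks age, and protocol 5.1 says tic severity is worst between 7 and 15 years and then declines.

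**Working it through.** **Inputs from the documents.** 98 subjects aged 6 to <18, randomized 1:1; 49 events; hazard ratio 0.4; 85% power; two-sided alpha 0.05; relapse "65% in the placebo group and 34% in the ecopipam group" (SAP 4.3). Interim at 34 events; final two-sided alpha 0.0492 (SAP 13). Visits at Weeks 13, 14, 15, 16, 18, 20, 22 and 24.

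**The plan's own figure.** Freedman: events = ((1+0.4)/(1-0.4))² × (1.960+1.036)² = 5.444 × 8.98 = 48.9, so 49. It reproduces. Power is 85.1% at 0.05 and 84.9% at 0.0492. Schoenfeld's formula would need only 43 events and gives 89.4% power with 49, which helps explain why simulated power exceeds 85%. The relapse proportions give 49×0.65 + 49×0.34 = 48.5 events and an implied hazard ratio of ln(0.66)/ln(0.35) = 0.396, consistent with the plan.

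**Assumptions.** The weight effect and the weight mix are not in the documents. The hazard was multiplied by g per band, in both directions: g = 1, 1.25 (1.25⁵, about 3.1-fold across the bands) and 1.5 (1.5⁵, about 7.6-fold). Three mixes, lightest to heaviest: 5/20/20/35/12/8%, 10/30/25/25/7/3% and 3/12/15/35/20/15%. Illustrative pooled bands: ≤34, >34 to ≤68 and >68 kg.

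**Main simulation.** 20,000 trials per scenario, permuted blocks of 4 within the six bands, exponential times read at the visits, no dropout, two-sided 0.0492. Both arms were calibrated so that relapse averaged over bands is 65% and 34%. All tests were run on the same simulated trials. Change in power from stratifying, in percentage points:

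| Weight effect | Three pooled bands | Six bands |
|---|---|---|
| None | -0.2 to -0.4 | -0.7 to -0.8 |
| ×1.25 per band | +0.4 to +0.8 | -0.1 to +0.3 |
| ×1.5 per band | +2.0 to +2.4 | +1.8 to +2.2 |

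Unstratified power was 88.5% to 90.9% throughout. At ×1.5, three bands raised it from 90.0-90.9% to 92.1-93.1%. The paired simulation error was 0.08 to 0.14 point.

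**Null rejection** (nominal 4.92%, 49.5% relapse in both arms). At ×1.25: 4.4-4.8% unstratified against 4.8-5.0% with three bands. At ×1.5: 3.7-4.0% against 4.7-5.1%.

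**Sensitivity to the calibration.** If the within-band hazard ratio is held at 0.40, the ×1.5 gain is +2.7 to +3.6 points, but ecopipam relapse is then 36.3-36.8% and not the planned 34%. A second set of runs also held it at 0.40, with six unpooled strata, two-sided 0.05, and two mixes (the first mix above, and equal bands). Power, unstratified to stratified:

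| Lightest-to-heaviest spread | First mix | Equal mix |
|---|---|---|
| 1 | 88.6% to 87.6% | 87.7% to 86.8% |
| 2 | 87.6% to 87.1% | 87.6% to 87.7% |
| 4 | 87.2% to 88.1% | 86.3% to 88.7% |
| 8 | 85.3% to 88.3% | 80.9% to 87.7% |

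Unstratified type I error in these runs fell from 5.0-5.1% at no spread to 2.7-3.6% at eight-fold; stratified, it was 4.4-5.5%.

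**Sparseness**, with events in proportion to subjects. The smallest of six bands holds 3% to 5% of subjects: 1.47 to 2.45 of 49 events, or 1.0 to 1.7 of 34. The smallest of three pooled bands holds 10% to 20%: 4.9 to 9.8 of 49, or 3.4 to 6.8 of 34.

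**The case against.** The strongest reply is that nothing is broken. The unstratified test is valid, protocol and SAP agree, both looks use one statistic, and calibrated power already exceeds 85%. The bands exist to reach a common mg/kg dose and to package drug, which is a dosing reason to stratify and not a prognostic one. The assumed treatment effect is 2.5-fold (1/0.4); even a 3.1-fold weight gradient buys less than one point, and gains of 2 points in the calibrated runs need a gradient that no passage supports. All of this stands, and it is why the point is put as an improvement.

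Three narrower objections also have substance.

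- The simulated pooling is not the example rule proposed below. Simulated directly, that rule gave -0.2 to -0.5 point with no weight effect and +0.3 to +0.6 at 3.1-fold (error about 0.2), so the conclusion does not change.
- A stratified Cox model estimates a within-band hazard ratio, which is a somewhat different quantity and should be described as such.
- The interim statistic, the 10.1.1 analysis and the all-ages secondary analysis were not simulated, nor was dropout, and the runs fixed the number of subjects although the trial is event-driven.

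None of these gives a reason to ignore the randomization strata.

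**Conclusion.** The point holds as a low-cost improvement. The primary, sensitivity, secondary and interim analyses do not use the strata of the randomization, and no reason is stated. With three pooled bands the exposure is about half a point of power if weight is not prognostic: 0.2 to 0.4 in the main runs, and up to 0.7 in smaller repeat runs with simulation error of 0.2 to 0.5. The return is about 2 points if weight is strongly prognostic, with the null rejection rate brought back close to nominal. A moderate weight effect gains less than one point. These sizes depend on assumed weight effects and mixes, and on no dropout. The trial's conclusions are not at risk from the current plan.

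**What to change.** Before any unblinded look:

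1. Stratify the log-rank test and the Cox model by weight band in SAP 10.1, 10.1.1 and 10.2.1, and state that the hazard ratio is within band.
2. Prespecify a blinded rule for pooling sparse adjacent bands, for example merging neighbours until each stratum has at least 5 events counted over both arms. Fix the pooling before the interim and keep it at the final analysis.
3. In SAP 13, define the interim statistic as Z = Σₖ(Oₖ-Eₖ)/√(ΣₖVₖ), summed over strata k, so that both looks use the same stratified statistic.
4. Keep the unstratified test as a sensitivity analysis.
5. Align protocol 13.4.1 and the synopsis, or record the change in SAP 14. Check SAP 7.1, 10.2.8, 10.2.21 and 10.2.22 for consistency, since they name or restate the same methods.

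The cost is text edits and programming. No new data are needed and the 49 events do not change. The price if weight is not prognostic is the fraction of a point given above, or 0.7 to 1.0 point if all six bands are kept unpooled. The documents do not say whether the interim has taken place; if it has, the stratified analysis should be supplementary only. If the sponsor prefers the unstratified test, one sentence giving the reason would close the gap.

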### 10.1.1. Sensitivity Analysis

To assess the robustness of the primary efficacy analysis, the following sensitivity analysis will be performed for the mITT and the ITT set:

Assume subjects who are lost to follow up or who discontinue the study for reasons other than Relapse or lack of efficacy meet the Relapse criteria. Their last non-missing date on study will be used as the date of Relapse. Relapse rate will be estimated using Kaplan-Meier methods and the difference between treatment arms will be tested using the log rank test. Cox proportional hazard model will be run with treatment as factor.

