7.5. Criteria for Subject Study Discontinuation

A subject may elect to discontinue from the study at any time for safety or personal reasons. All subjects who discontinue from the study should complete the early termination procedures.

Any subject with a new positive response on questions 4 and/or 5 of the Columbia Suicide Severity Rating Scale (C-SSRS) will be immediately discontinued and evaluated for risk.

Any subject with a CDRS-R or PHQ-9 assessment indicative of the onset of a new depressive episode at any visit can be discontinued from study participation at the discretion of the

Protocol EBS-101-TD-301 Version 9.0, 05 March 2024

Investigator. The Investigator will perform suicide risk assessment in subjects who respond positively to PHQ-9 question 9.

Subjects will be discontinued due to attempted suicide or suicidal behavior, oculogyric crisis, neuroleptic malignant syndrome, new onset seizures, serotonergic syndrome, or tardive dyskinesia. Subjects will also be discontinued if there are any adverse events that are Grade 4 (life-threatening consequences; urgent intervention indicated) in severity per CTCAE version 5.

Subjects who discontinue early from the study will be evaluated for one of these primary reasons: AE(s), lost to follow-up, subject choice, inadequate therapeutic effect, loss of efficacy, and administrative/other. In addition to the primary reason, the subject may have indicated one or more of these reasons as secondary reasons for discontinuation. Study disposition information will be collected on the CRF.

Subjects who discontinue treatment for any reason, other than an SAE (even if the SAE is not treatment related) or an AE (unless the AE can be determined to be unrelated to treatment), may be replaced only after consultation with Sponsor or its designee

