The CGI-TS-S endpoints currently listed as time-to-event exploratory endpoints may be considered as secondary endpoints, if there is a strong correlation between subjects meeting Relapse criteria based on YGTSS-TTS and those who also had at least a 1-point reduction on CGI-TS-S. The strong correlation would suggest Relapse is not a competing risk. Details will be provided in the Statistical Analysis Plan.

The time-to-event estimand for the primary endpoint, which uses the mITT study population, and for the time-to-event secondary and exploratory endpoints related to Relapse will rely on a treatment policy strategy (which also has elements of a composite strategy, in that three intercurrent events, initiation of additional medications and hospitalization for worsening symptoms are incorporated as part of the definition of the primary endpoint). The intercurrent events of loss to follow-up will be assumed unrelated to treatment and treated in estimation as censored observations. Sensitivity analyses for the primary endpoint may assess alternate treatment of such missing data; details will be provided in the Statistical Analysis Plan.

The time-to-event endpoints not related to Relapse will rely on a treatment policy strategy. A cumulative incidence approach will be used to account for the competing risk of study discontinuation due to Relapse. Cause-specific Cox models will be used to obtain the hazard ratio and its 95% CI for time to worsening. In this model, subjects who complete or discontinue from the double-blind randomized withdrawal period before meeting endpoint criteria and for reasons not related to Relapse will be censored at the time of discontinuation. In addition, we will consider graphical and descriptive approaches in correlating the YGTSS with other scores (e.g., CGI-TS-S) in the study subjects across time points.

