#### Intercurrent events:

The intercurrent events of initiation of additional medications to treat symptoms of TD and requirement of hospitalization for worsening symptoms of TD are included in the definition of Relapse and are considered a Relapse. The intercurrent event of loss to follow-up will be assumed unrelated to treatment and treated in estimation as censored observations. The intercurrent event of death will be handled as follows: if judged unrelated to blinded treatment or TD, death will be treated in estimation as a censored observation; if death is judged as related to blinded treatment or TD then it will be considered a Relapse. Judgement on whether a death is related to blinded treatment will be made prior to data unblinding. Data from subjects who complete or discontinue from the double-blind R/WD period without Relapse will be considered as censored observations.

Population-level summary: The time from Randomization to Relapse between the ecopipam and placebo treatment groups will be tested using a log rank test in the mITT population after having applied the treatment policy strategy specified above.

The primary efficacy analysis approach is in line with the primary estimand. Potential confounders will be identified and sensitivity and/or supplementary analysis may be used to deal with missing data and assess the robustness of conclusions.

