#### Statistical analysis:

An exploratory analysis will be performed on all randomized subjects in R/WD period to find time from randomization to study or treatment discontinuation. The analysis method will be similar to the primary efficacy analysis as described in Section 10.1. Data from subjects who complete the study will be considered as censored observations. The log rank test will be the primary test of statistical significance. Kaplan-Meier curves will be used to compare the times to treatment discontinuation between the treatment groups. The hazard ratio and its 95% confidence interval (CI) will be estimated from the Cox proportional hazard model with treatment as a factor. All observed endpoint data will be used in this analysis, without imputation.

10.2.22. Time from Randomization (Week 12) to loss of ≥ 100% of the improvement experienced on the YGTSS-TTS from Baseline (Day 1) to the last visit (Week 12) in the open-label Stabilization period for ecopipam compared to placebo.

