#### 10.2.25. Sensitivity Analysis

For exploratory endpoints of mean change, the difference in means between treatment arms in change from Randomization (Week 12) to Week 24 or from Baseline (Day 1) to Week 24, a sensitivity analysis may be performed. For the intercurrent events of study treatment discontinuation due to lack of efficacy, treatment related adverse events, death prior to Week 24 and Relapse for subjects with no assessment at

This document is confidential.

SAP text Version: SAP text 3.0 6-Dec-2023

Controlled Document ID: 3903A.02, Effective Date 31-Aug-2020

Week 24, the non-collected data of assessment at Week 24 will be multiply imputed using similar subjects (relevant demographic/baseline characteristics) from the placebo arm.

For example, the exploratory efficacy analysis on change in the YGTSS-TTS from Randomization (Week 12) to week 24 (Weeks 13, 14, 15, 16, 18, 20, 22 and 24) is to use MMRM model using all observed data. This model is appropriate when data are missing at random (MAR). To assess the robustness of the primary efficacy analysis, the following additional sensitivity analyses for missing data will be included for the mITT set:

- 1. Missing at Random (MAR) predictive mean matching multiple imputation method
- 2. Missing Not at Random (MNAR) jump to reference multiple imputation method
- 3. Tipping point under MNAR assumption

Details of sensitivity analysis for missing data and the statistical model are explained below.

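### Lack-of-efficacy exits that fall short of Relapse are censored in the primary analysis and again in its only specified sensitivity analysis, which turns other dropouts into Relapses

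*SAP*

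**What the plan says.** Relapse has three components (SAP 7.1 and 10.1): loss of at least half of the YGTSS-TTS improvement, added medication for Tourette's symptoms, or hospitalization for worsening symptoms. Leaving for lack of efficacy is not one of them.

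For the primary analysis, SAP 10.1 states: "Data from subjects who complete or discontinue from the double-blind R/WD period without Relapse will be considered as censored observations". SAP 7.1 repeats the rule. Its only exception is a death judged related to blinded treatment or the disorder, which counts as Relapse.

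SAP 10.1.1 specifies one sensitivity analysis, run in the mITT and ITT sets. It assumes that subjects lost to follow-up or "who discontinue the study for reasons other than Relapse or lack of efficacy meet the Relapse criteria", dated at the last study date. Beyond this, Protocol 13.4.1 says "Sensitivity analyses for the primary endpoint may assess alternate treatment of such missing data", and SAP 7.1 says "sensitivity and/or supplementary analysis may be used to deal with missing data". Neither names a further analysis.

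Two other places treat lack of efficacy as distinct from Relapse. Protocol 7.5 lists among its discontinuation reasons "inadequate therapeutic effect, loss of efficacy, and administrative/other". For the exploratory mean-change endpoints, SAP 10.2.25 opens a list that has Relapse as a separate item with "For the intercurrent events of study treatment discontinuation due to lack of efficacy", and allows imputation of those missing Week 24 values from placebo.

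**The concern.** The log-rank test and Kaplan-Meier curves assume that a censored subject has the same future risk as those who remain. That is least credible for someone who leaves because symptoms are returning. A sensitivity analysis of the censoring rule should stress that group first. SAP 10.1.1 does the opposite: an administrative dropout becomes a Relapse, and a loss-of-efficacy dropout stays censored.

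The check can therefore agree with the primary result when counting these exits would not, and the agreement would be read as robustness. The wording is also loose. Neither efficacy reason in Protocol 7.5 uses the SAP's term, so two programmers could code the same exit differently.

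**Working it through.** **1. Event status of a subject who leaves without meeting Relapse**

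| Reason for leaving | Primary (SAP 7.1, 10.1) | SAP 10.1.1 |
|---|---|---|
| Lost to follow-up | censored | Relapse |
| Adverse event, subject choice, administrative | censored | Relapse |
| Lack of efficacy | censored | censored |

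No other passage makes the last row an event. The ITT and per-protocol reruns change the analysis set, not the censoring rule. The multiple-imputation and tipping-point analyses in SAP 10.2.25 use YGTSS-TTS mean change. SAP 10.2.21 sets out "to find time from randomization to study or treatment discontinuation", but it is exploratory and pools every reason.

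**2. The plan's own figures**

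SAP 4.3: "The planned number of Relapse events for the double-blind R/WD Phase is 49 in children and adolescents", for 85% power at a hazard ratio (HR) of 0.4 and two-sided alpha 0.05. Freedman's formula gives (1.960 + 1.036)² × (1.4/0.6)² = 48.9, so 49 events. With 49 subjects per arm, Relapse proportions of 34% and 65% give 49 × 0.34 + 49 × 0.65 = 48.5 Relapses, taken here as 17 and 32. These figures are not in dispute; they set the scale.

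**3. Illustration on a fixed data set**

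- From the documents: 49 per arm, 17 and 32 Relapses, R/WD visits at weeks 1, 2, 3, 4, 6, 8, 10 and 12 after randomization, final two-sided level 0.0492.
- Assumed: Relapse times follow exponential curves reaching 34% and 65% at 12 weeks; 3 other dropouts per arm, spread evenly; x efficacy exits not meeting Relapse, timed like their arm's Relapses.
- Formulas: z = (O − E)/√V and one-step HR = exp[(O − E)/V], with O, E and V the observed, expected and variance terms for ecopipam.

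With 7 exits, all on ecopipam:

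| Analysis | Events | O | E | V | z | p | HR |
|---|---|---|---|---|---|---|---|
| Primary | 49 | 17 | 26.58 | 11.11 | −2.87 | 0.0041 | 0.42 |
| 10.1.1 as written | 49 + 6 = 55 | 20 | 29.83 | 12.28 | −2.81 | 0.0050 | 0.45 |
| 10.1.1, exits counted | 55 + 7 = 62 | 27 | 33.65 | 13.63 | −1.80 | 0.072 | 0.61 |

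Other splits (p-values):

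| Exits, ecopipam / placebo | Primary | As written | Counted |
|---|---|---|---|
| 3 / 0 | 0.0023 | 0.0027 | 0.011 |
| 6 / 0 | 0.0033 | 0.0040 | 0.043 |
| 7 / 2 | 0.0024 | 0.0029 | 0.025 |
| 3 / 3 | 0.0011 | 0.0013 | 0.0014 |
| 2 / 4 | 0.0006 | 0.0007 | 0.0003 |

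Significance at 0.0492 is lost at 7 ecopipam-only exits (7/49 = 14% of the arm). If all leave at one time, the number is 5 at R/WD week 2 (p = 0.053), 6 at week 4 (0.065), 7 at week 6 (0.068) and 9 at week 10 (0.054). With other dropouts split 4 ecopipam to 2 placebo, 4 exits give 0.0114 as written and 0.0503 counted. That case sits on the line: moving dropout times to the next visit gives 0.044. With 4 exits on placebo only, the HR goes from 0.34 (primary) to 0.32 (counted).

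**4. Simulation**

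3,000 trials per row, 10% other dropout per arm over 12 weeks (assumed). Each cell shows power at the 1.96 cut-off and mean HR.

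| Efficacy exits, ecopipam / placebo | Primary | As written | Counted |
|---|---|---|---|
| 5% / 5% | 87%, 0.41 | 81%, 0.47 | 79%, 0.49 |
| 15% / 15% | 86%, 0.41 | 80%, 0.47 | 72%, 0.54 |
| 15% / 5% | 87%, 0.40 | 81%, 0.46 | 59%, 0.58 |
| 20% / 5% | 87%, 0.40 | 81%, 0.46 | 46%, 0.64 |
| 5% / 15% | 85%, 0.42 | 79%, 0.48 | 87%, 0.46 |

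The analysis as written stays near 80% throughout, so it barely registers efficacy exits. Counting them moves power between 46% and 87%.

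**The case against.** **The group may be small.** Leavers should have an early-termination visit with a YGTSS, and added medication or hospitalization is Relapse whatever the score. The 50% rule can also be a low bar: a subject with baseline 20 and the minimum 25% response improved by 5 points and relapses on losing 2.5. This stands as a limit on size. It does not close the gap, because Protocol 8.3 asks for end-of-study procedures only where possible, and the threshold scales with response. A subject who went from 32 to 12 must lose 10 points; losing 9 and leaving for loss of efficacy is censored in both analyses.

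**The adverse cases are one-sided.** This also stands. The plan expects about twice as many Relapses on placebo. If efficacy exits follow that ratio, counting them strengthens the result, and even 7 against 2 stays significant. But the direction is unknown in advance, which is a reason to fix the rule now.

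**The authors may have regarded these exits as already Relapses.** Possible, but no passage says so, and Protocol 7.5 and SAP 10.2.25 list them apart from Relapse.

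**The CRF may use the SAP's term.** SAP 10.2.2 cites pregnancy as a captured reason, which Protocol 7.5 does not list, so the two lists may differ. The coding point is therefore conditional; the exemption is not.

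**An imbalance would be visible.** SAP 9.1 tabulates discontinuation reasons during R/WD. That shows a count, not its effect on the comparison.

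**A separate run adds little.** With balanced other dropouts this is nearly true: 0.042 and 0.070 at 6 and 7 exits, against 0.043 and 0.072. With the 4-to-2 dropout split and 4 exits it gives 0.023 against 0.050, so it separates the two sources.

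**Conclusion.** The concern holds and should be fixed. As written, the only specified check on the primary censoring rule exempts the exits most likely to be informative and would not reveal their effect. In the illustration, 7 ecopipam-only exits (5 to 9 depending on when they occur) remove significance when counted, while the analysis as written still reports p = 0.0050. With equal numbers on both arms almost nothing changes; with an excess on placebo the result strengthens. Exit counts, timing and other dropout rates are all assumptions, because the documents give none, so neither the size nor the direction in this trial can be predicted. The reading of the text does not depend on them. The primary test, its alpha and the 49-event target are not in question.

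**What to change.** Amend SAP 10.1.1 before unblinding:

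1. Delete *or lack of efficacy*, so that a discontinuation for inadequate therapeutic effect or loss of efficacy without Relapse counts as Relapse on the last study date.
2. Name the CRF discontinuation reasons treated as efficacy-related.
3. Add one run in which only those discontinuations become Relapse and other dropouts stay censored.

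The cost is a wording change and one more Kaplan-Meier, log-rank and Cox run. Protocol 7.5 already has disposition information collected on the CRF. The primary analysis, alpha and event target do not change.
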